1 LIST OF ABBREVIATIONS AND DEFINITIONS

| | |
|---------------|---|
| AI | Artificial intelligence |
| AUC | Area under the receiver operating characteristics curve |
| CE | Conformité Européenne |
| CI | Chief investigator |
| CIP | Clinical investigation plan |
| CNN | Convolutional neural network |
| CNORIS | Clinical negligence and other risks indemnity scheme |
| CRF | Case report form |
| CRN | Clinical research network |
| CT | Computed tomography |
| CTU | Clinical trials unit |
| CQC | Care Quality Commission |
| DICOM | Digital imaging and communications in medicine |
| DMC | Data management committee |
| DPIA | Data protection impact assessment |
| ED | Emergency department |
| EPR | Electronic patient record |
| FDA | (US) Food and Drug Administration |
| GCP | Good clinical practice |
| GDPR | General data protection regulation |
| GSTT | Guy's and St Thomas' Trust |
| HL7 | Health level seven |
| HSCN | Health and social care network |
| ICF | Informed consent form |
| IMP | Investigational medical product |
| ISO | International Organisation for Standardisation |

| | |
|---------------|--|
| ISRCTN | International standard randomised control trial number |
| LPAC | Local privacy advisory committee |
| MHRA | Medicines and Healthcare Regulatory Authority |
| NCCT | Non-Contrast Computed Tomography |
| NHSGGC | National Health Service Greater Glasgow and Clyde |
| NICE | The National Institute for Health and Care Excellence |
| PACS | Picture archiving and communication system |
| PPI | Patient and Public Involvement |
| QALY | Quality-adjusted life-year |
| QEUH | Queen Elizabeth University Hospital |
| REC | Research ethics committee |
| RIS | Radiology information system |
| SAE | Serious adverse event |
| SADE | Serious adverse device effect |
| SaMD | Software as a medical device |
| SMG | Study management group |
| SOP | Standard operating procedure |
| SSP | System security policy |
| SWAN | Scottish wide area network |
| TFA | Theoretical framework of acceptability |
| TMG | Trial management group |
| TSC | Trial steering committee |
| VPN | Virtual private network |

2 SUMMARY/SYNOPSIS

| | |
|---|---|
| Title | A mixed methods study to assess the clinical effectiveness and acceptability of qER artificial intelligence software to prioritise CT Head interpretation |
| Protocol Short Title/Acronym | Assess the Clinical Effectiveness in Prioritising CT Heads (ACCEPT) |
| IRAS Number | 313507 |
| REC Reference | TO BE COMPLETED BEFORE SUBMISSION |
| EDGE reference | 141791 |
| Study Duration | 14 months |
| Health condition(s) or problem(s) studied | Radiological Turn-around-time (TAT) of Head-NCCT scan reporting |
| Primary objective | To assess if qER (an artificial intelligence-based prioritisation software for non-contrast CT (NCCT) head scans) tool-based reporting and triage significantly reduces report turnaround time (TAT) of prioritised NCCT head scans for patients attending the emergency department. |
| Secondary objective (s) | 
 • To assess utility of qER to support emergency department pathways for patients requiring NCCT head and radiology reporting workflow. • To assess the safety of qER at identifying patients with critical findings on NCCT heads. • To evaluate the technical performance of qER. • To conduct a Health Economic, cost utility analysis of qER. |
| End of study definition | The end of the study is defined as the end of the 28 days follow-up of the last patient undergoing CT within study period. Final data analysis shall follow this. |
| Number of Participants | About 16,800 Head-NCCT scans from patients presenting to ED department during the study period. |
| Study Type | Observational |
| Human Tissue Samples (if applicable) | Not applicable |
| Data collected/storage (if applicable) | Data will be collected and stored only within the internal participating sites |

3 INTRODUCTION

3.1 Rationale

Emergency Department CT Head Pathway – meeting a need.

A non-contrast head CT (NCCT) is the first line imaging investigation for patients presenting to the emergency department (ED) for a variety of indications including, head injuries, non-traumatic intracranial haemorrhage and strokes. These scans are predominantly interpreted by a radiologist to guide management. Prompt diagnosis results in earlier treatment, reducing brain injury, mortality and illness¹. Rising ED attendances and concurrent radiologist shortage have resulted in increased wait times and workload^{2,3}. This has inadvertently led to higher demands for shorter report turnaround time in an effort to streamline throughput and decrease healthcare expenditures. Furthermore, for time-critical diagnoses like head injuries and strokes, an artificial intelligence (AI) tool which prioritises certain patients' NCCTs for earlier attention, could improve triage and improve patient outcome. Therefore, integrating such a tool in the radiologist workflow could allow for more rapid diagnosis and reporting of these critical conditions, enhancing the triage of patient the appropriate level of care.

The pressures on radiology departments

Diagnostic imaging plays a critical role in the management of ED patients and delays related to imaging are associated with longer hospital stays. As demand for acute care has risen and imaging equipment becomes more readily available, there has been a sustained rise in the demand for acute imaging. An independent review of the NHS England diagnostic service conducted by Sir Mike Richards has recommended doubling the number of scanners to reduce delays⁴.

Currently, most scans are interpreted by radiologists, but the Royal College of Radiologists (RCR) are predicting a shortage of 2000 NHS radiologists by 2023⁵. Image reporting turnaround times are now a major bottleneck for EDs. An RCR national audit showed <50% of ED patients receive their scan reports within the recommended time⁶ and only 2% of radiology departments can fulfil their reporting requirements within contracted hours.

AI – the opportunity

The potential applications of AI in radiology go well beyond image analysis for diagnostic and prognostic opportunities. It is becoming increasingly clear that AI algorithms have the potential to improve productivity, operational efficiency, and accuracy in diagnostic radiology. AI tools are being developed to aide diagnosis and enhance processes at multiple point in the radiology workflow including: (a) protocolling the prioritised scan, (b) clinical decision support systems for detection of critical findings, (c) worklist priority adjustment via AI results, and (d) reducing turnaround time through worklist prioritisation and semiautomated structures reporting. The adoption of AI tools is dependent on the demonstration of a tangible effect on patient care and improvement in radiologist workflow. Thus, in this study, we aim to assess whether real-world implementation of an AI tool which augments (b), (c) and (d) of the imaging life cycle would affect turnaround times.

qER

qER, a CE Class II approved medical software device, detects, and localizes the presence of six target abnormalities - intracranial haemorrhage, cranial fracture, midline shift, mass effect, atrophy and hypodensities suggestive of infarcts in non-contrast Head-CT scans⁷. A priority status is assigned if any one of the target abnormalities (intracranial haemorrhage, cranial fracture, midline shift or mass effect) is detected by the software, and the user will be able to view a single summary slice listing all the target abnormalities found by qER on the CT scan followed by all slices in scan with the overlay of above abnormalities localization. Alternately, if none of the target abnormalities are detected, the output will indicate that the software has analysed the image and identified no critical findings. qER reports are intended to support certified radiologists and/or licensed medical practitioners for clinical decision making. It is a support tool and, when used with original scans, can assist the clinician to improve efficiency, accuracy, and turnaround time in reading head CTs. It is not to be used to provide medical advice, determine treatment plan, or recommend a course of action to the patient.

3.2 Study hypothesis

Implementation of the qER product will reduce time to reporting of prioritised NCCT head findings requested through the Emergency Department and improve radiology reporting workflow, enabling improved Emergency Department clinical pathways for patients requiring NCCT imaging.

4 PATIENT AND PUBLIC INVOLVEMENT

Patient representatives and groups have contributed to protocol writing and will continue to be integral members of the team for wider dissemination. PPI leads will also be part of the Trial Management Group (TMG).

5 TRIAL OBJECTIVES AND PURPOSE

The purpose of this research is to test the hypothesis that implementation of the qER product in Emergency Department will reduce time to reporting of critical NCCT head findings requested through the Emergency Department and improve radiology reporting workflow, enabling improved Emergency Department clinical pathways for patients requiring NCCT imaging.

5.1 Definition of Terms

For the purpose of this study, there are custom terms specific to the qER device which are used throughout this document. The table below lists these terms and the corresponding definitions.

| Term | Definition |
|------------------------------|---|
| Target abnormality | 
This refers to the list of all target abnormalities that qER can detect in a Head NCCT scan. These are:
 
 • Intracranial haemorrhage • Midline shift • Mass effect • Cranial fracture • Atrophy • Hypodensities suggestive of infarct |
| qER prioritised findings | 
A subset of target abnormalities which when identified in a Head NCCT scan by qER will lead to the prioritisation of such scans in the radiology workload.
 
 • Intracranial haemorrhage • Midline shift • Mass effect • Cranial fracture |
| qER non-prioritised findings | 
A subset of target abnormalities which are detected by qER but not in the list of qER-prioritized findings:
 
 • Atrophy • Hypodensities suggestive of infarct 
These scans will not get prioritized in the radiology workload for interpretation by the Trust radiologist but will still be available for interpretation in the workload in a non-prioritized manner.
 |
| qER no findings | 
Any Head NCCT scans where none of the target abnormalities are identified by qER will be classified as scans where no qER findings are identified
 |
| qER not interpreted | 
Head NCCT scans which were not processed by qER and thus have no AI outputs
 |

5.2 Primary Objective

To assess if qER (an artificial intelligence-based prioritisation software for Head-NCCT scan findings) tool-based reporting and triage significantly reduces report turnaround time (TAT) of prioritised NCCT head scans for patients attending the emergency department.

5.3 Secondary Objectives

- To assess utility of qER to support emergency department pathways for patients requiring NCCT head and radiology reporting workflow.
- To assess the safety of qER at identifying patients with critical findings on NCCT heads
- To evaluate the technical performance of qER
- To conduct a Health Economic, cost utility analysis of qER.

6 STUDY DESIGN & FLOWCHART

6.1 Study Design

6.1.1 Summary

A multi-centre stepped wedged cluster randomised study (Figure 1) will be conducted in 4 NHS hospitals over a 13-month period. Hospitals will be identified and initiated into the qER solution with a 30-day implementation period. The order in which sites will receive the qER intervention will be determined by computer-based randomisation. The stepped wedge design allows delivery of the intervention at an organisational level with evaluation of outcome measures at a patient level. Structuring the implementation through a staged activation in a random order provides important methodological advantages for both qualitative and quantitative elements of the study. The design allows control of adoption bias and adjust for time-based changes in the background patient characteristics at a patient level.

[figure not shown]

Figure 1: illustration of site initiation within the stepped-wedge design. Each square block represents a duration of 1 month.

6.1.1.1 Pre-Implementation

During the pre-implementation phase, data will be collected to support the primary and secondary outcomes as this will constitute the baseline data for analysis.

6.1.1.2 Implementation

The thresholds for detecting target abnormalities will be adjusted, if necessary, during the implementation phase as per the deployment SOP for qER. Data from this implementation phase will not be used for analysis of primary and secondary outcomes pertaining to the utility of qER.

6.1.1.3 Post-Implementation

The implementation of new healthcare practices and the adoption of AI technologies is not linear. Study design and the elements of the study will enable evaluation of broadly the performance of the AI technology, acceptability, and the economic costs of adoption.

This randomised stepped wedge healthcare service delivery study to assess the clinical effectiveness of qER to prioritise patients reporting of NCCT scans that have prioritised findings (identified from AI analysis of a CT). The study will have an unaided (without qER

implemented) and aided phase (with qER implemented). During the unaided phase the reporting of CT will follow the same workflow as in the current standard of care (i.e., the images/cases will appear in the RIS chronologically and the radiologist either follows this order or prioritise some cases based on communication from ED). When the radiologist clicks a case in RIS, a secondary capture of qER along with the original images will be available in PACS.

During the post-implementation phase there will be a notification (prioritised flag) in RIS. The order of the cases in RIS will not be altered. When the radiologist clicks a case in RIS, a secondary capture of qER along with the original images will be available in PACS. This secondary capture will have contour showing the algorithm's attention point. The radiologist can choose to agree with qER findings as it or modify or ignore it according to their clinical judgement, writing and signing off the report. For scans which were not processed by qER the radiologist can prioritise and report as per the standard of care.

For the purposes of technical evaluation of qER, the scans taken during the aided phase will be divided into four categories:

- Scans with qER prioritised findings (prioritised pathway)
- Scans with qER non-prioritised findings (qER non-prioritised pathway)
- Scans not flagged as having no qER findings (qER no finding pathway), and
- Not interpreted (scans not processed by qER, Not interpreted pathway)

In the qER prioritised, qER non-prioritised and qER no finding pathway, all cases where the radiologist did not agree with qER findings will be sent for ground truthing (2+1 method, Figure 2). A random sample of 500 scans will also be sent for ground-truthing process for the purpose of technical evaluation.

[figure not shown]

Figure 2: Post-implementation workflow

[figure not shown]

Figure 3: Example of current and proposed pathways for patients undergoing Head-NCCT scans from the Emergency Department.

“qER finding” workflow.

This will involve scans where qER identifies one or more of the target abnormalities which includes prioritised and non-prioritised findings. qER offers the opportunity to optimise NCCT finding detection. The study will integrate qER into ED clinical pathways (Figure 3). Images from ED pathway will be interpreted by qER and those identified to having the presence of any one or more of the prioritised findings will be flagged to radiologist for ‘prioritised’ reporting (allocated to duty radiologist). Along with the prioritised flag, radiologists can be provided with a secondary DICOM series with a contour that outlines the abnormality identified by qER. Following review, a radiology report will be generated and prioritised findings communicated to the ED clinician through existing escalation pathways. For scans where only non-prioritised finding have been detected by qER, they will also be flagged appropriately so that the reporting radiologist is informed of the same.

“No qER findings” workflow

qER also supports the workflow by ruling out target abnormalities. All images identified as absence of finding will be reviewed and reports verified.

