6.1.2 Hospital Sites

Participating hospitals must undertake a significant number (3000) of NCCT Head within the Emergency Department per annum. Specialty leads from radiology and Emergency Department will be identified with support from their NHS Trust/Board to participate in the deployment of qER. Hospitals that have already deployed qER or similar AI-enhanced NCCT head will be excluded. Sites were identified that provide good representation of potential heterogeneity (geographical, population, ethnicity, population age).

An independent statistician will perform a computerised randomisation of the clusters and keep randomisation records prior to the beginning of the data collection. Simple randomisation will be used to randomise one trust to receive the intervention in each of the

time periods. Local investigators will be notified ~6 weeks in advance of activation qER tool at their hospital.

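### The protocol gives control-phase radiologists a qER secondary capture in the same paragraph that defines the control as standard of care without qER

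*Protocol*

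**What the plan says.** Protocol section 6.1.1.3 divides the stepped-wedge study into an unaided phase, before qER is in place, and an aided phase, once it is. On the unaided phase it says: "During the unaided phase the reporting of CT will follow the same workflow as in the current standard of care". A parenthesis explains that cases appear in RIS in time order and that the radiologist follows that order or moves cases forward at the request of the emergency department. The paragraph then goes on to put a qER output in PACS for the reader: "based on communication from ED). When the radiologist clicks a case in RIS, a secondary capture of qER along with the original images".

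A new paragraph opens on the post-implementation phase. It introduces a priority flag in RIS and continues: "The order of the cases in RIS will not be altered. When the radiologist clicks a case in RIS, a secondary capture of qER", finishing in the same words as before. It adds that this capture carries a contour showing where the algorithm's attention lies.

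The control condition has two uses elsewhere. Section 6.2 compares the primary outcome, time from acquisition to report for patients with prioritised findings, with standard of care. Section 6.1.1.1 says that in the pre-implementation phase "data will be collected to support the primary and secondary outcomes as this will constitute the baseline data for analysis".

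**The concern.** The two statements about the unaided phase cannot both be true. If qER is not in place, there is no qER output to open. If a qER capture is shown when the case is opened, reporting does not follow the current standard of care.

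The sentence sits in the paragraph that tells sites how control reporting works. A site that took it literally could conclude that both phases include a capture and that only the RIS flag and the contour are new after activation. The primary contrast would then be flag plus contour against capture alone, not qER against standard of care. The baseline for the primary and secondary outcomes would not be usual care either. Control periods exposed in this way could not be recovered afterwards.

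**Working it through.** No figure is involved beyond a word count, so the check is a comparison of texts.

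**1. Where the sentence falls.** The secondary-capture sentence runs from the radiologist clicking a case to availability in PACS and has 23 words. It occurs twice in section 6.1.1.3 with identical wording. The first occurrence follows directly on the description of unaided reporting, before the post-implementation phase is introduced. The second comes after the RIS flag, in the post-implementation paragraph.

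**2. Can it be read as a remark about both phases?** Yes, but the conflict remains, because radiologists would still see qER output in a phase defined as having none.

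**3. What the rest of the protocol implies about the control.**

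- Section 6.1.1: "Hospitals will be identified and initiated into the qER solution with a 30-day implementation period". qER arrives at a site's step.
- Section 6.1.1.2: "The thresholds for detecting target abnormalities will be adjusted, if necessary, during the implementation phase as per the deployment SOP for qER". Tuning takes place at the step, not before it.
- Section 6.1.2: "Hospitals that have already deployed qER or similar AI-enhanced NCCT head will be excluded". Usual care at an eligible site therefore has no qER output.
- Section 6.1.2: "Local investigators will be notified ~6 weeks in advance of activation qER tool at their hospital". There is a defined activation point.
- Section 8.2: pre-implementation data describe the existing clinical pathway.
- Section 15.1: each site switches from the standard pathway to the intervention.
- Sections 6.5.1 and 6.5.3: the economic comparison is between current care and care that includes qER.

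All of these agree on a control without qER. The first occurrence of the sentence is the outlier, and accidental copying from the next paragraph explains it best.

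**4. Does any visible text withdraw the sentence?** No. The passages in step 3 imply that no capture exists before activation, but none says that qER output is withheld from control readers. Figures 1 to 3 and the Appendix 4 flowchart are not shown and may depict the intended workflow.

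**5. Could qER run during control periods?** The protocol does not say that unaided scans are processed in the background. Appendix 5, section 5.4.2, marks the qER receipt time, report time, probability scores and scan category as mandatory, with no restriction by phase in the visible text. The scan category does have a code for scans that were not processed, so this does not show that background processing is planned. It does make visibility of output a fair configuration question.

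**6. Size.** Section 15.1 powers the study for a 20% reduction in turnaround time. The protocol does not divide that effect between the flag, which acts in RIS, and the capture, which acts once the case is open. With no input for the capture's own effect, in size or sign, no bias, power loss or number of affected scans can be calculated.

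**The case against.** The strongest reply is that the protocol as a whole leaves no real doubt. Beyond the passages on site selection and activation, section 15.1 names the control as the standard pathway. Section 6.1.1, under the heading on the qER finding workflow, presents the secondary series as accompanying the priority flag, and section 6.1.1.3 places that flag after implementation. A site with no activated qER has nothing to generate a capture. On this view one misplaced sentence is an editorial slip with no demonstrated consequence.

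A second reply is that even the literal reading leaves much of the contrast intact. The outcome runs from acquisition to report, the flag acts on the wait before a case is opened, and only the reading stage would be shared. The statement in section 3.1 that qER can improve turnaround time in reading describes intended use and is not an effect assumption for this trial.

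Much of this stands. A copied sentence is the likeliest cause, contamination is not shown to have occurred, and the prioritisation contrast would not vanish. Two things do not follow. The other passages show which reading was probably meant, but they do not correct the sentence. And because it lies in the description of the comparator for the primary outcome, following it would change what is being compared, so it is more than clerical.

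**Conclusion.** The concern holds. Section 6.1.1.3 is wrong as written: it defines the unaided phase as free of qER and following standard of care, then gives its readers a qER output. It should be fixed.

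The size of the consequence cannot be derived, and no bias is claimed to have occurred. If the sentence were followed, and if the capture shortens reading as section 3.1 suggests it can, the difference between phases would shrink. Without that premise even the direction is open.

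The conclusion rests on the visible text alone. The missing figures and flowchart could confirm which workflow was intended, but the contradictory sentence would still need correcting.

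**What to change.** Reconcile the two paragraphs of section 6.1.1.3 by removing the secondary-capture sentence from the description of the unaided phase and keeping it for the post-implementation phase. Check the result against Figures 1 to 3 and the Appendix 4 flowchart.

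Add one statement that no qER output, whether flag, capture or report, is visible to reporting radiologists before activation at their site, including where unaided scans are processed in the background for analysis. Deleting the sentence alone would leave that case open.

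Confirm PACS routing at each of the four sites before the control period begins.

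The cost is a sentence-level protocol correction and a configuration check at four sites, with no additional patients or data.
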